6.2.2.4 Causality of Adverse Events

The principal investigator will assess the causal relationship between BOS161721 or placebo and the AE. One of the following categories ([Table 4](#)) should be selected based on medical judgment, considering the definitions below and all contributing factors.

Table 4. Causality Definitions

Related	A clinical event, including laboratory test abnormality, occurs in a plausible time relationship to treatment administration and which concurrent disease or other drugs or chemicals cannot explain. The response to withdrawal of the treatment (dechallenge ^a) should be clinically plausible. The event must be definitive pharmacologically or phenomenologically, using a satisfactory rechallenge ^b procedure if necessary.
Unrelated	A clinical event, including laboratory test abnormality, with little or no temporal relationship with treatment administration. May have negative dechallenge and rechallenge information. Typically explained by extraneous factors (eg, concomitant disease, environmental factors, or other drugs or chemicals).

^a Dechallenge: Upon discontinuation of a drug suspected of causing an AE, the symptoms of the AE disappear partially or completely, within a reasonable time from drug discontinuation (positive dechallenge), or the symptoms continue despite withdrawal of the drug (negative dechallenge). Note that there are exceptions when an AE does not disappear upon discontinuation of the drug, yet drug relatedness clearly exists (for example, as in bone marrow suppression, fixed drug eruptions, or tardive dyskinesia).

^b Rechallenge: Upon re-administration of a drug suspected of causing an AE in a specific patient in the past, the AE recurs upon exposure (positive rechallenge), or the AE does not recur (negative rechallenge).

An unexpected adverse drug event is any adverse drug event for which the specificity or severity is not consistent with the current IP.

6.2.2.5 Seriousness of Adverse Events

An SAE is defined as any untoward medical occurrence that at any dose:

- Results in death
- Is life threatening; this means that the patient was at risk of death at the time of the event; it does not mean that the event hypothetically might have caused death if it were more severe
- Requires hospitalization or prolongation in existing hospitalization
- Results in persistent or significant incapacity or substantial disruption of the ability to conduct normal life functions
- Is a congenital anomaly or birth defect
- Is other important medical event (see below)

Important medical events that do not result in death, are not life threatening, or do not require hospitalization may be considered SAEs when, based on appropriate medical judgment, they may jeopardize the patient and may require medical or surgical intervention to prevent 1 of the outcomes listed in this definition. Examples of such events are:

- Intensive treatment in an emergency room or at home for allergic bronchospasm
- Blood dyscrasias or convulsions that do not result in inpatient hospitalization
- Development of drug dependency or drug abuse

Hospitalization for elective surgery or routine clinical procedures that are not the result of AE (eg, elective surgery for a pre-existing condition that has not worsened) need not be considered SAEs. If anything untoward is reported during the procedure, that occurrence must be reported as an AE, either 'serious' or 'nonserious' according to the usual criteria.

Suspected unexpected serious adverse reactions (SUSARs) are AEs that are associated with the use of the drug and are serious and unexpected.

6.2.2.6 Adverse Events of Special Interest

AEs of special interest in this study include the following:

1. Anaphylaxis and serious allergic reactions
2. Grades 2 to 5 injection site reaction, including erythema, pain, and induration (See [APPENDIX 6](#))
3. Drug Induced Liver Injury (DILI) assessed following Hy's Law
4. Malignancy (not including basal cell carcinoma or squamous cell carcinoma of skin)
5. Opportunistic infections such as disseminated histoplasmosis, cryptococcosis, disseminated herpes simplex, disseminated tuberculosis, *Aspergillus* sp., *Candida albicans*, *Coccidioides immitis*, *Cryptococcus neoformans*, *Cytomegalovirus*, *Histoplasma capsulatum*, *Isospora belli*, and *Polyomavirus JC polyomavirus*
6. Cryptosporidiasis

6.2.2.6.1 Anaphylaxis and Serious Allergic Reactions

Anaphylaxis will be defined according to the National Institute of Allergy and Infectious Diseases/Food Allergy and Anaphylaxis Network (NIAID/FAAN) criteria.⁴² In the event of anaphylactic reaction or severe/serious hypersensitivity/allergic reaction, the patient must discontinue IP and emergency resuscitation measures implemented. In case of other mild to moderate hypersensitivity reaction, depending on the severity, the investigator may manage in accordance with the standard-of-care.

Anaphylaxis is highly likely when any one of the following 3 criteria is fulfilled:

1. Acute onset of an illness (minutes to several hours) with involvement of the skin, mucosal tissue, or both (eg, generalized hives, pruritus, or flushing, swollen lips-tongue-uvula) and at least 1 of the following:
 - a. Respiratory compromise (eg, dyspnea, wheeze-bronchospasm, stridor, reduced peak expiratory flow [PEF], hypoxemia)
 - b. Reduced blood pressure or associated symptoms of end-organ dysfunction (eg, hypotonia [collapse], syncope, incontinence)
2. Two or more of the following that occur rapidly after exposure to a likely allergen for that patient (minutes to several hours):
 - a. Involvement of the skin-mucosal tissue (eg, generalized hives, itch-flush, swollen lips-tongue-uvula)

- b. Respiratory compromise (eg, dyspnea, wheeze-bronchospasm, stridor, reduced PEF, hypoxemia)
 - c. Reduced blood pressure or associated symptoms (eg, hypotonia [collapse], syncope, incontinence)
 - d. Persistent gastrointestinal symptoms (eg, crampy abdominal pain, vomiting)
3. Reduced blood pressure after exposure to known allergen for that patient (minutes to several hours):
- a. Systolic blood pressure of less than 90 mm Hg or greater than 30% decrease from the patient's baseline

6.2.2.6.2 Injection Site Reactions

Injection site reactions are to be captured and reported as AEs. These will include Grades 2 to 5 injection site erythema, pain, and induration (see [APPENDIX 6](#)), which are also captured as Adverse Events of Special Interest (See [Section 6.2.2.6](#)). The investigator should provide a clear description of the observed or reported AE including location and severity. All concomitant treatments used to treat injection site reactions should be recorded and captured in the eCRF, together with the AE of injection site reactions.

6.2.2.6.3 Potential Drug-Induced Liver Injury

Abnormal values in AST and/or ALT levels concurrent with abnormal elevations in total bilirubin level that meet the criteria outlined below in the absence of other causes of liver injury are considered potential cases of DILI, and as potential Hy's Law cases, and should always be considered important medical events. If symptoms compatible with DILI precede knowledge of serum chemical test abnormalities, liver enzyme measurements should be made immediately, regardless of when the next visit or monitoring interval is scheduled. In some cases, symptoms may be an early sign of injury and although typically less sensitive than serum enzyme elevations, they may indicate a need for prompt serum testing. An increase in liver enzymes should be confirmed by a repeated test within 48 to 72 hours following the initial test, prior to reporting of a potential DILI event. Patients will continue to have weekly or biweekly liver enzyme measurements until resolution or levels return to baseline.

All occurrences of potential DILIs, meeting the defined criteria, must be reported as SAEs (see [Section 6.2.2.7.2](#) for reporting details).

Potential DILI is defined as:

1. ALT or AST elevation $> 3 \times$ ULN

AND

2. Total bilirubin $> 2 \times$ ULN, without initial findings of cholestasis (elevated serum alkaline phosphatase)

AND

-
3. No other immediately apparent possible causes of ALT or AST elevation and hyperbilirubinemia, including, but not limited to, viral hepatitis, pre-existing chronic or acute liver disease, or the administration of other drug(s) known to be hepatotoxic

The patient should return to the investigational site and be evaluated as soon as possible, include laboratory tests, detailed history, and physical assessment. In addition to repeating measurements of AST and ALT, laboratory tests should include albumin, CK, total bilirubin, direct and indirect bilirubin, GGT, prothrombin time (PT)/International Normalized Ratio (INR), and alkaline phosphatase. A detailed history, including relevant information, such as review of ethanol, acetaminophen, recreational drug and supplement consumption, family history, occupational exposure, sexual history, travel history, history of contact with a jaundiced person, surgery, blood transfusion, history of liver or allergic disease, and work exposure, should be collected. Further testing for acute hepatitis A, B, or C infection and liver imaging (eg, biliary tract) may be warranted. All cases confirmed on repeat testing as meeting the laboratory criteria defined above, with no other cause for liver function test (LFT) abnormalities identified at the time should be considered potential Hy's Law cases irrespective of availability of all the results of the investigations performed to determine etiology of the abnormal LFTs. Such potential Hy's Law cases should be reported as SAEs.

Study drug discontinuation is considered if there is marked serum AST or ALT elevation or evidence of functional impairment (as indicated by rising bilirubin or INR, which represent substantial liver injury) that is related to study drug. Discontinuation of treatment should be considered if:

- ALT or AST $> 8 \times$ ULN
- ALT or AST $> 5 \times$ ULN for more than 2 weeks

Discontinuation of treatment must occur if:

- ALT or AST $> 3 \times$ ULN and (total bilirubin $> 2 \times$ ULN or INR > 1.5)
- ALT or AST $> 3 \times$ ULN with the appearance of fatigue, nausea, vomiting, right upper quadrant pain or tenderness, fever, rash, and/or eosinophilia ($> 5\%$)

6.2.2.6.4 Malignancy

The identification of a malignancy event will be made by the study site and communicated to the sponsor or designee. AEs should be reported as serious per the criteria in [Section 6.2.2.5](#).

After the first dose of study drug, when there is a decision to biopsy a potentially malignant tumor, lymph node, or other tissue (with the exception of suspected basal cell/squamous cell), the investigator and/or consultant(s) should contact the sponsor clinicians or designee to discuss the issue and any decisions as soon as possible. Basal cell carcinoma or squamous cell carcinoma of skin is not considered an AE of special interest.

6.2.2.6.5 Specific Infections

Any diagnosis or suggested diagnosis of opportunistic infections such as disseminated histoplasmosis, cryptococcosis, disseminated herpes simplex, disseminated tuberculosis, *Aspergillus* sp., *Candida albicans*, *Coccidioides immitis*, *Cryptococcus neoformans*, *Cytomegalovirus*, *Histoplasma capsulatum*, *Isospora belli*, or *Polyomavirus JC polyomavirus* will be recorded as AEs of special interest.

Cryptosporidiosis is also considered an AE of special interest. Patients will be evaluated for cryptosporidium in the stool at screening, and as clinically indicated (eg, watery diarrhea) during the study. If a patient develops diarrhea during the study a stool sample must be provided to test for ova, parasites, and cryptosporidium.

6.2.2.7 Reporting of Adverse Events

AE reporting will be carried out in accordance with applicable local regulations, including regulatory agency and IRB reporting requirements.

Each AE is to be assessed to determine if it meets the criteria for an SAE. If an SAE occurs, expedited reporting will follow local and international regulations, as appropriate, and is further outlined in [Section 6.2.2.7.2](#).

6.2.2.7.1 Reporting of Pregnancy

As information is available, a pregnancy diagnosed during the study will be reported within 24 hours to the sponsor via the Pregnancy Notification and Outcome Form, including pregnancy in female patients who received study drug and female partners of male study patients who received study drug. The pregnancy should be followed to term and/or outcome and this outcome should also be reported to the sponsor via the Pregnancy Notification and Outcome Form. Pregnancy itself is not regarded as an AE or SAE unless there is complication.

In the case of a live birth, the structural integrity of the neonate can be assessed at the time of birth. In the event of a termination, the reason(s) for termination should be specified and, if clinically possible, the structural integrity of the terminated fetus should be assessed by gross visual inspection (unless pre-procedure test findings are conclusive for a congenital anomaly and the findings are reported).

If the outcome of the pregnancy meets the criteria for an AE or SAE (ie, ectopic pregnancy, spontaneous abortion, intrauterine fetal demise, neonatal death, or congenital anomaly [in a live born, a terminated fetus, an intrauterine fetal demise, or a neonatal death]), the investigator should follow the procedures for reporting SAEs.

Additional information about pregnancy outcomes that are reported as SAEs follows:

- Spontaneous abortion includes miscarriage and missed abortion
- Neonatal deaths that occur within 1 month of birth should be reported, without regard to causality, as SAEs. In addition, infant deaths after 1 month should be reported as serious

adverse events when the investigator assesses the neonatal death as related or possibly related to exposure to investigational product.

6.2.2.7.2 Reporting of Serious Adverse Events

The principal investigator is responsible for providing notification to the sponsor of any SAE via the Safety Adverse Event Form, whether deemed study drug related or not, that a patient experiences during their participation in this study within 24 hours of becoming aware of the event.

If an SAE is fatal or life threatening, notification to the sponsor must be made aware immediately, irrespective of the extent of available AE information. This timeframe also applies to additional new information (follow-up) on previously forwarded SAE reports as well as to the initial and follow-up reporting of exposure during pregnancy and exposure via breastfeeding cases. In the rare event that the investigator does not become aware of the occurrence of an SAE immediately (eg, if an outpatient study patient initially seeks treatment elsewhere), the investigator is to report the event within 24 hours after learning of it and document the time of his/her first awareness of the AE.

The principal investigator will review each SAE and evaluate the intensity and the causal relationship of the event to the study drug. All SAEs will be recorded from the time of first dose of study drug through the safety follow-up period (up to Day 270). SAEs occurring after the final follow-up visit and coming to the attention of the principal investigator must be reported only if there is (in the opinion of the principal investigator) reasonable causal relationship with the study drug.

As a minimum requirement, the initial notification should provide the following information:

- Study number
- Patient number
- Details of the SAE (verbatim details are sufficient for immediate notification)
- Criterion for classification as ‘serious’
- Causality assessment (which may be updated in a follow-up report when sufficient information is available to make this classification)

Initial reports of SAEs must be followed later with detailed descriptions, including clear photocopies of other documents as necessary (eg, hospital reports, consultant reports, autopsy reports, etc), with the study patient’s personal identifiers removed. All relevant information obtained by the principal investigator through review of these documents will be recorded and submitted to the sponsor within 24 hours of receipt of the information. If a new Safety Adverse Event Form is submitted, then the principal investigator must sign and date the form. The sponsor may also request additional information on the SAE, or clarification of omitted or discrepant information from the initial notification, which the principal investigator or an authorized delegate should submit to the sponsor within 24 hours of the request as possible.

6.2.2.7.3 Reporting of Adverse Events of Special Interest

AEs of special interest will be reported to safety immediately or within 24 hours of the site becoming aware of the event and recorded as such on the Adverse Events eCRF and Safety Adverse Event Form.

Potential DILI will be reported based on specifications mentioned in [Section 6.2.2.6.3](#).

Each AE of special interest is to be assessed to determine if it meets the criteria for an SAE. If an SAE occurs, expedited reporting will follow local and international regulations, as appropriate, and is further outlined in [Section 6.2.2.7.2](#).

6.2.2.8 Follow Up of Adverse Events

All AEs will be followed up through the safety follow-up visits. All SAEs experienced by a patient, irrespective of the suspected causality, will be monitored until the event has resolved, until any abnormal laboratory values have returned to baseline or stabilized at a level acceptable to the principal investigator and medical monitor, until there is a satisfactory explanation for the changes observed, or until the patient is lost to follow-up.

See [Section 6.2.2.7.1](#) for details related to follow-up of pregnancy. See [Section 6.2.2.6.3](#) for details related to follow-up of potential DILI. See [Section 6.2.2.6.4](#) for details related to follow-up of malignancy.

6.2.3 Vital Signs

Vital signs (blood pressure, heart rate, and body temperature) will be assessed as specified in the Schedule of Assessments ([Section 3.4](#)). Vital signs will be assessed on Day 0 at predose and at Day 0, 1 and 2 hours postdose, as well as on each of the scheduled visit days during the study (excluding PK-only site visits). Supine BP and heart rate recordings will be made after the patient has been recumbent and at rest ≥ 5 minutes. When the timing of these measurements coincides with a blood collection, vital signs should be obtained prior to the time of the blood collection.

6.2.4 12-Lead Electrocardiograms

ECG will be assessed as specified in the Schedule of Assessments ([Section 3.4](#)). ECG recording will initiate after the patient has been supine for at least 5 minutes. On days of PK blood draws, the ECG will be collected before scheduled PK blood draws, though timing will be such that PK draws are collected on their scheduled times where possible.

The ECG will include all 12 standard leads and a Lead II rhythm strip on the bottom of the tracing. The ECG will be recorded at a paper speed of 25 mm/second. The following ECG parameters will be collected: PR interval, QRS interval, RR interval, QT interval, and QT interval corrected for heart rate using Fridericia's formula (QTcF).

All ECGs must be evaluated by a qualified physician or qualified designee for the presence of abnormalities and will be captured electronically and retained for future evaluation if required, up to the time of the clinical study report (CSR) completion.

6.2.5 Physical Examinations

The full physical examination will be completed at screening and Day 0. It includes an assessment of general appearance and evaluation of head, eyes, ears, nose, mouth, throat, neck, thyroid, lymph nodes, and extremities, and dermatologic, respiratory, cardiovascular, gastrointestinal, musculoskeletal, neurologic, and psychiatric systems.

The targeted (limited) physical examination will be completed at all other visits as indicated in the Schedule of Assessments ([Section 3.4](#)). It includes evaluation of patient complaints and SLE disease-related issues, and will exclude the genitourinary system.

6.2.6 C-SSRS

The C-SSRS is a low-burden measure of the spectrum of suicidal ideation and behavior that was developed by Columbia University researchers for the National Institute of Mental Health Treatment of Adolescent Suicide Attempters Study to assess severity and track suicidal events through any treatment. It is a clinical interview providing a summary of both ideation and behavior that can be administered during any evaluation or risk assessment to identify the level and type of suicidality present. The C-SSRS can also be used during treatment to monitor for clinical worsening.⁴³

The C-SSRS evaluation will be performed as specified in the Schedule of Assessments ([Section 3.4](#)). Patients with recent (within the past 12 months) or active suicidal ideation or behavior based on patient responding “yes” to question 3, 4, or 5 is exclusionary at screening will be excluded from the study. Patients with recent or active suicidal ideation or behavior at subsequent study visits will have responses to the C-SSRS reviewed in detail to assess patient risk, and appropriate consultative mental health services will be provided.

6.2.7 Injection Site Reactions

Patients will be monitored for local injection site reactions as specified in the Schedule of Assessments ([Section 3.4](#)). Local injection site reactions will be assessed at 2 hours postdose at baseline, and predose for each injection after baseline. Injection site reactions should be managed according to the standard of care. Injection site reactions, Grades 2 to 5, are to be reported as AEs of special interest (see [Section 6.2.2.7.3](#)).

6.2.8 Immunogenicity

The serum samples to measure the presence of ADA will be collected as specified in the Schedule of Assessments ([Section 3.4](#)). Blood samples (4 mL) to provide approximately 1.5 mL of plasma for anti BOS161721 antibody analysis will be collected into appropriately labeled tubes containing K₂EDTA. The presence or absence of ADA will be determined in the serum samples using validated bioanalytical methods. Blood samples for ADA analysis will be

collected up to Day 90 from all patients. Subsequent ADA samples will be collected from all patients but only analyzed by a central lab if the patient had a positive ADA on Day 90.

After the first dose, if a patient tests positive in the validated confirmatory ADA assay, a sample from this patient will be further analyzed in the neutralizing antibody (nAb) assay by a central lab.

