2.1 Phase 1b Multiple Ascending Dose

OBJECTIVES	ENDPOINTS
Primary	

 To assess safety, tolerability, and immunogenicity of repeat doses of BOS161721 (20, 60, and 120 mg) administered SC in adult patients with moderately to severely active SLE on limited background standard of care treatment, in order to estimate the optimal dose. 	Safety Endpoints 
 Incidence and severity of AEs and SAEs, related AEs, AEs leading to study drug discontinuation, AEs by severity and relatedness Injection site reactions Columbia Suicide Severity Rating Scale (C-SSRS) 12-lead ECGs parameter results at each visit and change from baseline Vital signs (blood pressure [BP], heart rate, and temperature) parameter results at each visit and change from baseline Clinical laboratory results and change from baseline Physical examinations changes from baseline ADAs Study drug exposure/compliance
Secondary	

 To characterize the PK of BOS161721 and select the optimal dose of BOS161721 based on safety, PK, and PD effects in patients with moderately to 	Pharmacokinetic Endpoints 
 BOS161721 concentration by visit and time point Maximum observed concentration (C_{max}), T_{max}, area under the concentration-time curve (AUC), terminal elimination

severely active SLE.
	
half-life ($t_{1/2}$), systematic clearance (CL), volume of distribution (V_d)
 
Pharmacodynamic Endpoints
 
 • Results and changes (or shifts) from baseline to each visit in phosphorylated signal transducer and activator of transcription 3 (pSTAT3), C3 and C4 levels, and leukocyte immunophenotype • Results and changes (or shifts) from baseline in anti-double-stranded DNA (dsDNA), antinuclear antibodies (ANA), anti-Sjögren syndrome A and B (SSA, SSB), Smith (Sm), and antiphospholipid (APL) autoantibodies at each visit • Results and changes (or shifts) from baseline in abrogation of IL-21 gene signature at each indicated visit

Exploratory
	

 • CCI [REDACTED] 	
 • CCI [REDACTED] • CCI [REDACTED]

 • CCI [REDACTED] 	
 • CCI [REDACTED]

 • CCI [REDACTED] 	
 • CCI [REDACTED]

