3 STUDY PLAN

3.1 Study Design

This is a Phase 1b/2 combined, randomized, multicenter, double-blind, placebo-controlled trial to study the clinical efficacy, safety, and PK of SC doses of BOS161721 in adult patients with moderately to severely active SLE. After successfully completing a screening phase, eligible patients will be randomized to a specified dose of BOS161721 or placebo. The dosing schedule will be monthly.

The trial will consist of 2 double-blinded portions: MAD Phase 1b and POC Phase 2. Patients may receive a total of 7 SC monthly doses of study drug on Days 0, 30, 60, 90, 120, 150, and 180, followed by safety follow-up visits at Days 210, 240, and 270.

SLE disease activity assessment data will be centrally reviewed by medical monitor and sponsor to ensure the scores are clinically meaningful and compliant with specific definition. The scope of responsibility includes, but is not limited to, review and confirmation of “A” and “B” BILAG system organ disease, confirmation of clinical components of the SLEDAI-2K score at screening and during the study, and cross-validation of the instruments used in this study to assess the disease activity. Further details on the content and methods of data reports by the medical monitor and sponsor will be outlined in the Medical Data Review Plan along with the processes and procedures that will be followed.

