ⁱ SLEDAI-2K should be done before randomization and dosing on Day 0 as SLEDAI-2K < 6 is exclusionary.

^j Clinical laboratory assessments will include a fasting glucose and lipid panel, with exception of screening (Visit 1) which will be nonfasting.

^k When clinically indicated for hemolytic anemia.

^l Blood samples for ADA analysis will be collected up to Day 90 from all patients. Subsequent ADA samples will be collected from all patients but only assayed (analyzed) if the patient had a positive ADA on Day 90.

^m nAb is collected for all patients, though will only be analyzed by central lab if patient is positive for ADA at Day 90.

ⁿ Only CCI collected during safety follow-up visits.

^o Urine pregnancy test will be collected on WOCBP prior to study drug administration on dosing visits.

^p Cryptosporidium test is required at screening. If a patient develops diarrhea during the study a stool sample must be provided to test for ova, parasites, and cryptosporidium.

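### ADA samples on Days 180 and 270 are assayed only in patients ADA-positive on Day 90, so ADA that first appears later is never measured

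*Protocol*

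**What the plan says.** In the current protocol (V5.0), Section 6.2.8 has ADA samples "collected up to Day 90 from all patients". Later samples are still drawn from everyone but are "only analyzed by a central lab if the patient had a positive ADA on Day 90". Table 1 footnote k (Phase 1b) and Table 2 footnote l (Phase 2) in Section 3.4 give the same rule: "Subsequent ADA samples will be collected from all patients but only assayed (analyzed) if the patient had a positive ADA on Day 90".

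The ADA rows of both tables show samples on Days 0, 15, 30, 60, 90, 180 and 270. Section 3.1 allows "a total of 7 SC monthly doses of study drug on Days 0, 30, 60, 90, 120, 150, and 180".

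The Phase 1b primary objective in Section 2.1 begins "To assess safety, tolerability, and immunogenicity of repeat doses of BOS161721", and ADAs are listed among the safety endpoints in Sections 2.1 and 2.2.

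For nAb testing there are two rules. Section 6.2.8 says "After the first dose, if a patient tests positive in the validated confirmatory ADA assay, a sample from this patient will be further analyzed" for nAb. Section 5.3 and Table 3 footnote g likewise require only ADA positivity. Table 1 footnote l and Table 2 footnote m say "nAb is collected for all patients, though will only be analyzed by central lab if patient is positive for ADA at Day 90".

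**The concern.** The rule treats a negative Day 90 result as settling a patient's ADA status for the rest of the study, although dosing runs to Day 180 and follow-up to Day 270. An analysis plan cannot repair this, because it cannot summarize results that the laboratory is told not to produce.

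Section 1.2.5 itself lists immune complex disease and altered drug levels or activity as possible consequences of ADA. The SRI-4 assessment on Day 210 lies between the two conditional samples, and the Phase 1b sampling after the last dose (Days 180 to 270) lies entirely in the uncovered period. If a patient negative on Day 90 had an unexpected fall in exposure, a hypersensitivity event or a loss of response in that period, there would be no ADA result to set beside it. The protocol makes no exception for such cases.

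**Working it through.** The plan states no ADA rate or precision target, so there is no figure to reproduce. The check is a count from the schedule, followed by an illustration.

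**Coverage for a patient negative on Day 90**
- Dosing days (Section 3.1): 0, 30, 60, 90, 120, 150, 180, which is 7 doses.
- Doses before Day 90: Days 0, 30 and 60, so 3 of 7. The ADA sample is not explicitly labelled predose, but a sample taken on Day 90 could not show a response to that day's dose either way. Four doses (Days 90, 120, 150, 180) are therefore not covered.
- ADA samples after Day 90: Days 180 and 270. Both depend on the Day 90 result.
- Time without an ADA result: (270 − 90) / 270 = 180 / 270 = 67% of the study period.

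**Direction of the error**
- Let A be the proportion first positive by Day 90, and L the proportion first positive later.
- Incidence through Day 270 is A + L. The plan can measure only A.
- The shortfall is L, which cannot be negative. Patients first positive on Days 15, 30 or 60 are included in A whatever their Day 90 result.

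**Illustration of what assaying all samples would show**
- Phase 2 active patients: 156 × 2/3 = 104 (Section 8.1).
- Chance of at least one late case = 1 − (1 − L)^104. The values of L are assumptions, and assay sensitivity is taken as perfect.

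| Assumed L | Expected late cases | Chance of at least one, all samples assayed | Chance under the written rule |
|---|---|---|---|
| 1% | 1.0 | 65% | 0 |
| 2% | 2.1 | 88% | 0 |
| 5% | 5.2 | 99.5% | 0 |
| 10% | 10.4 | >99.9% | 0 |

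**Added assays**
- Phase 2: 156 × 2 = 312.
- Phase 1b: 30 × 2 = 60.
- Total: at most 372. The true number is smaller, because patients positive on Day 90 are already assayed and some patients will drop out.

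**nAb trigger**
- While the Day 90 condition on ADA stands, the two nAb rules differ for patients positive on Day 15, 30 or 60 and negative on Day 90. Section 6.2.8 sends them for nAb testing and the footnotes do not.
- If the condition on ADA is removed and the nAb footnotes are left alone, the rules will also differ for patients first positive on Day 180 or 270.

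**The case against.** The case for leaving the rule alone is that it is deliberate, stated the same way in three places, and leaves the SRI-4 comparison, its significance level and its power untouched. In Phase 1b, immunogenicity is assessed to help estimate the dose. The dose review was planned for 30 days after the last Cohort 3 patient's third dose (Day 60 + 30 = Day 90), so later samples from the latest patients could not have informed it. In Phase 2, ADA is one of nine listed safety endpoints, and PK is collected at selected sites only, which already limits any link between ADA and exposure. All of this stands, and it lowers the weight of the point. It does not supply the missing results.

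A reader might infer more than the documents support:
- **That the later samples are discarded.** They are collected from everyone and conditionally assayed. Nothing says they are destroyed, so the gap may be recoverable.
- **That early positives who are negative on Day 90 are lost from incidence.** Samples through Day 90 carry no condition, so these patients count. Only their later course is missing.
- **That circulating drug masks Day 90 and makes Day 270 the most informative sample.** No drug tolerance is given for the assay. With simple one-compartment superposition (equal doses, complete absorption; an assumption) and the final half-life of 80 to 87 days in Section 1.2.2.3, residual drug on Day 270 is 92% to 98% of the Day 90 predose level. It falls to about 49% only with the interim 44-day half-life in Section 1.2.3.
- **That the Day 90 figure will be presented as a whole-study figure.** The protocol does not say how ADA incidence will be labelled.
- **That the shortfall can be quantified.** Any percentage would be assumed.

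**Conclusion.** The concern holds as a limit on what is measured. Followed as written, the plan gives ADA incidence for onset through Day 90, after 3 of 7 doses, and says nothing about later onset in patients negative on that day. As an estimate over full dosing and follow-up it can only be too low, by an unknown amount. The conclusion rests on the schedule and the assay rule alone; the table of late-onset rates is illustration. It bears on the Phase 1b primary objective and on a safety endpoint in both parts, and not on the primary efficacy test. The inconsistency in the nAb trigger is a separate, smaller defect that needs reconciling.

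**What to change.** - Delete the Day 90 condition on ADA from Section 6.2.8, Table 1 footnote k and Table 2 footnote l.
- Assay the Day 180 and Day 270 samples in all patients in both parts, including retained Phase 1b samples where still available.
- Report treatment-emergent ADA incidence through Day 270.
- Replace the two nAb triggers with one rule that has no Day 90 condition, amending Table 1 footnote l and Table 2 footnote m. Apply it to the nAb samples scheduled on Days 90 and 180, and to other ADA-positive samples where volume allows. nAb is scheduled only on those two days, and the protocol does not say that the ADA tube holds enough for both assays.

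The cost is the added ADA assays, at most about 312 in Phase 2 and 60 in Phase 1b, some further nAb assays, and an edit to the protocol and laboratory manual. No new visit or ADA blood draw is needed.
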